6.2.1.4 Reporting of Adverse Events

All AEs, regardless of severity and when they occurred (any time after the ICF is signed and through the Follow-up Period), are to be recorded. The Investigator should complete all the details requested including dates of onset, severity, action taken, outcome, relationship to study drug. Each event should be recorded separately.

6.2.1.5 Reporting of Serious Adverse Events

All SAEs will be recorded using the electronic data capture (EDC) system. The Investigator will be instructed to contact the Sponsor/designee for any questions on SAE reporting. Contact details will be provided per country, and per region (please refer to Study Manual for the appropriate information).

Urgent safety queries issued in EDC must be followed up and addressed within 1 business day. Follow-up information and response to non-urgent safety queries should be combined for reporting to provide the most complete data possible within each follow-up. In the event that the EDC system is unavailable, SAEs are to be reported by faxing/emailing the paper SAE Form to Quintiles using the appropriate fax number provided for each country or project safety mailbox.

6.2.1.5.1 Notification of Regulatory Authorities, Investigators, and Institutional Review Board/Independent Ethics Committee

Any SAE, including death due to any cause, which occurs during this study, whether or not related to the study drug, must be reported immediately (within 24 hours of the site's knowledge of the event). Additional information will be available in the Study Manual.

The report will contain as much available information concerning the SAE to enable the Sponsor (or an authorized representative) to file a report, which satisfies regulatory reporting requirements. These timelines apply to initial reports of SAEs and to all follow-up reports.

All SAEs during the 30 day follow-up period will be collected and reported as previously described.

6.2.1.5.2 Reporting of Serious Adverse Events to Regulatory Authorities and Investigators

Investigators will be notified by the Sponsor or Quintiles of all Serious Unexpected Adverse Event Reactions (SUSARs) that require prompt submission to their Institutional Review Board (IRB) or Independent Ethics Committee (IEC). Investigators should provide written documentation of IRB/IEC notification for each report to the Sponsor or Quintiles. The Sponsor or Quintiles will ensure that all SUSARs are reported to the appropriate regulatory authorities.

Noven Pharmaceuticals, Inc.
HP-3070-GL-04
HP-3070

56

6.2.1.6 Follow-up of Adverse Events

All AEs will be followed up to resolution. However, AEs and SAEs that are ongoing at the subject's last study visit (i.e., discharge from the clinic at the end of the double-blind treatment period or early termination) will be followed until resolution or for 30 days after last dose of study drug, whichever comes first. Resolution means that the subject has returned to a baseline state of health or the Investigator does not expect any further improvement or worsening of the AE. All AEs and SAEs that occur during the 30 day follow-up period should be reported to the Sponsor or Quintiles.

6.2.1.7 Pregnancy and Contraception

It is important that female subjects and the partners of male subjects do not become pregnant during the study.

Instructions for Male Subjects

All male subjects should avoid fathering a child by the use of an effective means of contraception (see below), unless their partner is not of childbearing potential, i.e. postmenopausal or permanently sterilized (e.g., tubal occlusion, hysterectomy, bilateral salpingectomy).

Male subjects (including men who have had vasectomies) whose partners are currently pregnant should use a condom for the duration of the study and for 1 month after the last patch is removed. This is to ensure that the fetus is not exposed to the drug product via the ejaculate.

Male subjects must not donate sperm for 3 months following the removal of the last patch. Males should continue using contraception for 1 month after the last patch is removed.

Instructions for Female Subjects

Female subjects must use contraception unless they are not of childbearing potential, i.e. postmenopausal or permanently sterilized (e.g., tubal occlusion, hysterectomy, bilateral salpingectomy). Sexually active females of child-bearing potential must agree to use a medically accepted method of contraception during the study and for 1 month after the final dose of study medication. Female subjects must not donate eggs for 3 months after the last patch is removed.

Acceptable forms of contraception

- Condom or occlusive cap (diaphragm or cervical/vault caps) with spermicidal foam/gel/film/cream/suppository;
- Established use of oral, injected or implanted hormonal methods of contraception;
- Established use of medically prescribed topically-applied transdermal contraceptive patch;
- Documented placement of an IUD or intra-uterine system (by female partner); and

Noven Pharmaceuticals, Inc.
HP-3070-GL-04
HP-3070

57

- Male sterilization (with the appropriate post-vasectomy documentation of the absence of sperm in the ejaculate).

The Sponsor/designee must be notified within 24 hours of the site's knowledge of any subject who becomes pregnant while participating in a clinical study. It is the responsibility of the Investigator, or designee, to report any pregnancy in a subject which occurs during the study by using the Pregnancy form.

Although pregnancy is not technically an AE, all pregnancies must be followed to conclusion to determine their outcome. This information is important for both drug safety and public health concerns. The Investigator should make every effort to follow the subject until completion of the pregnancy. If the outcome of the pregnancy meets the criteria for immediate classification as an SAE (i.e., post-partum complications, spontaneous abortion, stillbirth, neonatal death, or congenital anomaly, including that in an aborted fetus), the Investigator should follow the procedures for reporting SAEs.

6.2.2 Clinical Laboratory Evaluations

6.2.2.1 Clinical Laboratory Assessments

A central laboratory designated by the Sponsor will be used for all laboratory assessments during the trial. If an immediate result is required, a sample should be sent to both the local and central laboratory.

Urine samples and fasting blood samples will be collected from each subject as presented in [Table 1](#) (Schedule of Events). The clinical laboratory parameters evaluated in this study are presented in [Table 7](#).

Noven Pharmaceuticals, Inc.
HP-3070-GL-04
HP-3070

58

Table 7 Clinical Laboratory Tests

Hematology: WBC count with differential RBC count Hematocrit Hemoglobin Platelet count
 
Urinalysis: pH Specific gravity Protein Ketones Glucose Blood Microscopic exam (performed only if any part of the urinalysis is not negative)
 
Urine Drug Screens:^a Amphetamines Barbiturates Benzodiazepines Cannabinoids Cocaine Marijuana Methadone Opiates Phencyclidine Propoxyphene
 
Additional Tests (screening only): HIV HbsAg^d Anti-HCV^d Blood alcohol^e
	
Serum Chemistry: ALP ALT AST BUN CPK^f Creatinine LDH Total bilirubin Triglycerides Cholesterol (total, LDL, and HDL) Calcium Chloride Glucose Insulin Magnesium Bicarbonate Inorganic phosphorus Sodium Potassium Total protein Uric acid GGT Prolactin^b Albumin
 
Additional Tests: Urine pregnancy (women of child-bearing capacity)^c TSH (free T₄, if TSH is abnormal) HbA1c Alcohol breathalyzer test^g

--	---

ALP = alkaline phosphatase; ALT = alanine transaminase; AST = aspartate transaminase; BUN = blood urea nitrogen; CPK = creatine phosphokinase; GGT = gamma glutamyl transferase; HbA1c = hemoglobin A1c; HBsAg = Hepatitis B antigen; HCV = Hepatitis C Virus; HDL = high density lipoprotein; HIV = human immunodeficiency virus; LDH = lactic dehydrogenase; LDL = low density lipoprotein; RBC = red blood cell; TSH = thyroid stimulating hormone; WBC = white blood cell count.

- Urine drug screens may be done at the Investigator's discretion. If the subject is allowed to leave the unit, a urine drug screen must be done when the subject returns.
- The central laboratory will not report prolactin levels to the sites nor the Sponsor, because this could potentially result in unblinding the treatment. The central laboratory will report prolactin levels as "masked" on the laboratory report. See Section 6.2.2.2.3 for additional information.
- All positive urine pregnancy test results must be confirmed by a serum test. Subjects with positive urine and serum pregnancy test results at Screening must not be enrolled. Subjects with positive urine and serum pregnancy test results during the trial must discontinue treatment and be withdrawn from the trial. If the subject is allowed to leave the unit, a urine pregnancy test must be done when the subject returns.
- Subjects with chronic Hepatitis B or C may be included in the study provided that their condition is stable and that values for liver function tests and other laboratory tests results meet the criteria specified for entry into the study.
- A serum blood sample will be collected to test blood alcohol level at the screening visit.
- Reflex testing for urine myoglobin will be done in cases where CPK > 1000 U/L.
- If the subject is allowed to leave the unit, an alcohol breathalyzer test must be done when the subject returns.

Noven Pharmaceuticals, Inc.
HP-3070-GL-04
HP-3070

59

Clinical laboratory tests will be reviewed for results of potential clinical significance at each time point during the study. The Investigator will evaluate any change in laboratory values. If the Investigator determines a laboratory abnormality to be clinically significant, it is considered a laboratory AE; however, if the abnormal laboratory value is consistent with a current diagnosis, it may be documented accordingly.

6.2.2.2 Monitoring of Selected Laboratory Values

6.2.2.2.1 Liver Enzymes

Subjects should be closely observed if they meet the definition of Hy's Law cases, defined as:

- ALT or AST $>3 \times$ ULN AND
- Alkaline phosphatase (ALP) $<2 \times$ ULN AND
- increase in bilirubin $\geq 2 \times$ ULN

If the subject's laboratory results meet these criteria, the subject should be evaluated and repeat or additional testing should be performed. Elevations in liver enzymes that require discontinuation of the subject are presented in [Section 4.3.3](#). Potential Hy's Law cases should be reported as SAEs.

6.2.2.2.2 Neutrophil Counts

Subjects with an absolute neutrophil count of <1000 per mm^3 should have an additional test within 24 hours. If the values are not within normal limits or increasing, the subject will be discontinued from the study.

6.2.2.2.3 Prolactin

The central laboratory will not report the prolactin levels after baseline to the sites or Sponsor/designee, as this value could unblind the subject's treatment. The central laboratory will report prolactin levels as "masked" on the laboratory report. If an Investigator suspects hyperprolactinemia (due to symptoms or signs that could be attributed to a high prolactin level), a blood sample should be taken and sent to the central laboratory. Blood samples for prolactin levels should not be sent to the local laboratory.

If a subject's serum prolactin level is $>10 \times$ ULN, the site will be notified by the central laboratory and the Investigator will do a repeat blood draw within 3 days. If the subject's prolactin level is still $>10 \times$ ULN, the Investigator should consider other possible causes of hyperprolactinemia (e.g., primary hypothyroidism, chronic renal failure, cirrhosis, use of drugs [opiates, estrogens, cimetidine, etc.], pregnancy for female subjects).

If the laboratory requests a prolactin re-test, a "dummy" request will be sent for another subject at the same clinical site and the subject will be selected randomly in order to preserve the blind. Such cases will be discussed with the study Medical Advisor.

The Medical Advisor and site will remain blinded to the subject's treatment allocation.

Noven Pharmaceuticals, Inc.
HP-3070-GL-04
HP-3070

60

6.2.3 Vital Signs, Physical Findings and Other Safety Assessments

Height will be recorded at Screening, only. Weight will be recorded at each visit. A complete physical examination including examination of the head, neck, ears and throat, thorax, abdomen, urogenital, extremities, neurological, and skin and mucosae will be performed at Screening and at end of study. Abnormal physical examination findings at the Screening will be recorded as medical history and abnormal physical examinations findings at subsequent visits will be recorded as AEs.

Vital sign measurements will include temperature, systolic blood pressure (SBP), diastolic blood pressure (DBP), and heart rate. Blood pressures (sitting) and pulse rates should be measured after subject has rested (sitting quietly) for 5 minutes.

In addition, assessments for orthostatic hypotension will be performed. Blood pressure readings and pulse rate will be obtained after the subject has been supine for 5 minutes. These will be repeated after the subject has been standing up for approximately 1 to 3 minutes.

Subjects with a decrease of ≥ 30 mmHg in SBP and/or a decrease of ≥ 20 mmHg in DBP after ≥ 3 minutes standing compared with the previous supine blood pressure, OR development of symptoms are considered to have orthostatic hypotension.

Twelve-lead ECGs will be recorded at Screening and at the visits specified in [Table 1](#). An ECG recordings will be obtained after the subject has been supine and at rest for at least 5 minutes. Additional 12-lead ECGs may be obtained at the Investigator's discretion and should always be obtained if the subject discontinues the study. A central ECG service will be utilized for reading all ECGs in order to standardize interpretations for the safety analysis. In addition, ECG results will be evaluated at the investigational site to monitor safety during the trial. The Investigator or designee will review, sign, and date each ECG reading, noting whether or not any abnormal results are of clinical significance. The ECG will be repeated if any results are considered by the Investigator to be clinically significant.

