6.2.1 Adverse Events and Serious Adverse Events

6.2.1.1 Adverse Events

An AE is any untoward medical occurrence in a subject given study drug. The event does not necessarily have to have a causal relationship with this treatment. The recording of AEs will begin when the subject signs the ICF and will continue up to the 30 day follow-up period. AEs that are ongoing at discharge will be followed until resolution or for 30 days after the last dose of study drug, whichever comes first.

Noven Pharmaceuticals, Inc.
HP-3070-GL-04
HP-3070

52

An AE can be:

- Any unfavorable and unintended sign (including an abnormal laboratory finding), symptom, or disease temporally associated with the use of a medicinal product, whether or not considered related to the medicinal product.
- Any new disease or exacerbation of an existing disease.
- Any deterioration in non-protocol-required measurements of laboratory values or other clinical tests (e.g., ECG or X-ray) that results in symptoms, a change in treatment, or discontinuation of study drug.
- Recurrence of an intermittent medical condition (e.g., headache) not present at Baseline.

For the purpose of this study, in addition to the AE definitions described above the following definitions will also be used.

- Treatment-emergent depression defined a priori as a CDSS score ≥ 6 .
- Abnormalities in physical examination findings that require clinical intervention or further investigation (beyond ordering a repeat [confirmatory] test)
- Laboratory abnormalities that require clinical intervention or further investigation (beyond ordering a repeat [confirmatory] test) unless they are associated with a clinical event that has already been reported.
- Worsening in the subject's symptoms of schizophrenia or new symptoms will be considered AEs.
- Symptoms of other psychiatric disorders will be considered AEs if they are new (not part of the subject's medical history) or if their severity and/or frequency are greater than those noted in the subject's medical history.
- Overdose: An overdose is defined as the ingestion of study drug beyond the dosing regimen defined in the study protocol and/or an overdose of any other product. An overdose, and any symptoms resulting from the overdose, are considered AEs and should be recorded. An overdose will be considered an SAE if it meets the definition of an SAE described in Section 6.2.1.2.

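### Section 6.2.3 makes an abnormal physical finding after Screening an AE even if unchanged, and the protocol does not say which of its AE triggers for physical and laboratory findings governs

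*Protocol*

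**What the plan says.** **Physical findings.** Protocol section 6.2.3 schedules the complete physical examination, skin included, at Screening and at end of study. It then divides the findings by visit: "Abnormal physical examination findings at the Screening will be recorded as medical history", while "abnormal physical examinations findings at subsequent visits will be recorded as AEs". Neither half of the sentence sets a threshold or refers to change since Screening. Section 6.2.1.1 lists a narrower study-specific AE: "Abnormalities in physical examination findings that require clinical intervention or further investigation", where a repeat test alone does not count as investigation.

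**Laboratory findings.** Section 6.2.1.1 uses the same kind of trigger, "Laboratory abnormalities that require clinical intervention or further investigation", and exempts abnormalities tied to a clinical event that has already been reported. Section 6.2.2.1 uses a different one: "If the Investigator determines a laboratory abnormality to be clinically significant, it is considered a laboratory AE". Its exception also differs: "if the abnormal laboratory value is consistent with a current diagnosis, it may be documented accordingly".

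**General definition.** The first part of 6.2.1.1 counts any unfavorable, unintended sign, and names abnormal laboratory findings, with no threshold. The study-specific items are introduced as additions to it. No section gives an order of precedence.

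**The concern.** Taken as written, 6.2.3 can turn medical history into an AE. A scar, murmur or mild tremor noted at Screening and found again, unchanged, at Week 6 or early termination is an abnormal finding at a later visit and so qualifies. Elsewhere 6.2.1.1 works on a new-or-worse principle, for new or exacerbated disease and for symptoms of other psychiatric disorders. Section 6.2.3 departs from that.

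The several triggers add to the problem. A site that treats the 6.2.1.1 items as a filter, and a site that follows 6.2.3 or 6.2.2.1 to the letter, would both be following the protocol and would record different AEs from the same findings. AE incidence is a safety endpoint collected at approximately 70 centers. This is a data-collection rule, so an analysis plan cannot repair it fully: later analysis can filter what was recorded but cannot recover what a site did not record.

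**Working it through.** The plan states no expected AE count or rate, so there is no figure to reproduce and nothing to compute. The check sets the rules side by side and runs typical findings through them.

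| Finding | Section | Trigger | Exception |
|---|---|---|---|
| Physical | 6.2.1.1, study-specific | Needs action, or work-up beyond a repeat test | None |
| Physical | 6.2.3 | Abnormal at any visit after Screening | None |
| Laboratory | 6.2.1.1, study-specific | Needs action, or work-up beyond a repeat test | Tied to an event already reported |
| Laboratory | 6.2.2.1 | Investigator judges it clinically significant | Consistent with a current diagnosis |
| Either | 6.2.1.1, general | Any unfavorable, unintended sign | None |

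Four cases:

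1. *Physical finding in the history, unchanged at end of study, no action needed.* An AE under the letter of 6.2.3. It does not meet the study-specific item in 6.2.1.1.
2. *New, trivial physical finding at end of study, no action needed.* An AE under 6.2.3. It does not meet the study-specific item, though the general definition can cover it.
3. *Laboratory value judged clinically significant but only re-tested.* An AE under 6.2.2.1. It does not meet the study-specific laboratory item, though the general definition can cover it.
4. *Laboratory value that prompts further work-up but is not judged clinically significant.* An AE under the study-specific item, and under the general definition, but not under the 6.2.2.1 trigger.

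The number of recorded AEs therefore depends on which section a site follows.

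Next, what reaches the tables. Section 8.4.6 defines a treatment-emergent AE by onset on or after the start of study medication, or by earlier onset with increased severity. Section 8.6.1 requires first occurrence or worsening after the first administration. Case 1, dated correctly to before the first dose, fails both definitions; it enters the double-blind tables only if a site gives the examination date as the onset. Cases 2 to 4, with onset after the first dose, pass both definitions if they are recorded at all.

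Scope: the rule that sweeps in unchanged findings concerns physical examination only. With that examination scheduled at Screening and end of study, the later visits in question are in practice the Week 6 or early-termination examination and any unscheduled one.

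**The case against.** The strongest reply is that there is no contradiction. Section 6.2.1.1 never says that a finding is an AE only if it needs action. Its study-specific items widen a general definition that already covers abnormal laboratory findings, so all the rules can be read as a union. On that reading a clinically significant glucose or transaminase rise that needs no action is an AE under 6.2.1.1 as well as 6.2.2.1. As for stable findings, an AE is by definition an untoward occurrence, and 6.2.3 itself classes Screening findings as history, so a sensible site would not record them twice.

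Much of this stands. A reader might infer that 6.2.1.1 forbids what 6.2.2.1 and 6.2.3 require, and the text does not support that. But the union reading leaves the narrower thresholds with no work to do: after Screening, 6.2.3 already captures every abnormal physical finding, and the general definition captures every abnormal laboratory finding. A site that gives those thresholds meaning will use them as filters, and nothing tells it not to. The sensible reading of 6.2.3 also has to supply a condition that the sentence lacks.

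It is also fair to reply that the consequences are limited. Safety summaries are descriptive, with no significance tests. Section 8.6.2 summarises laboratory data directly by mean change, incidence of abnormal values and shift tables, and potential Hy's Law cases are reported as SAEs on numeric criteria. All of that stands.

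**Conclusion.** The point holds as a defect in recording rules, of minor weight. Section 6.2.3 lacks a new-or-worsened condition, and three sections give different triggers and exceptions without saying which governs. The expected result is noise and site-to-site inconsistency in descriptive AE counts. Its size cannot be derived from the protocol, which gives neither the prevalence of stable abnormal findings nor an expected AE rate.

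Two stronger conclusions are tempting and are not supported:

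- *That active-placebo differences in AE rates are diluted or biased.* Randomisation is stratified by country and assessment is blinded, so extra or missing records would be expected in all arms, and no differential mechanism is shown.
- *That stable findings would distort the list of AEs occurring in 5% or more of an arm.* AE incidence is tabulated by preferred term, while unchanged findings would scatter over unrelated terms. A total over all terms cannot be compared with a per-term cut, and correctly dated records do not enter the treatment-emergent tables.

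The verdict assumes that sites follow the text as printed. Training or eCRF instructions not shown here could narrow the inconsistency in practice.

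**What to change.** Amend the sentence in 6.2.3 to read: *abnormal physical examination findings that are new or worsened since Screening will be recorded as AEs*. Then reconcile 6.2.1.1, 6.2.2.1 and 6.2.3 so that one section states the AE trigger and any exceptions for each type of finding, consistent with the general AE definition, and the other sections cross-refer to it.

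The 6.2.3 sentence should not also require a finding to need action or work-up. That would stop new signs that need no action from being recorded there while the general definition still counts them, so it would narrow safety capture and create a fresh conflict.

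The cost is a small change to the protocol wording and the eCRF guide. The downside is that unchanged physical findings will appear only in the examination listings.
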